8.11.3 Storage

Serum samples will be sent for storage as soon after collection as possible within the Newcastle MRC Centre Biobank for Rare and Neuromuscular Diseases based at the Institute of Genetic of Medicine, Newcastle University.

Any samples remaining once the trial biomarker analysis has taken place will be banked for use in future bone disease or ER stress biomarker research, if the patient or their parent(s)/legal guardian(s) has consented to this.

It is the responsibility of the trial site to ensure that samples are appropriately labelled in accordance with trial procedures to comply with the applicable legislation (e.g. General Data Protection Regulation (GDPR)). Labelling requirements can be found in the trial Laboratory Manual. Biological samples collected from participants as part of this trial will be transported, stored, accessed and processed in accordance with national legislation relating to the use and storage of human tissue for research purposes and such activities shall at least meet the requirements as set out in the 2004 Human Tissue Act and 2006 Human Tissue (Scotland) Act.

8.12 End of Trial

The end of trial will be defined as the date of last data collection for the last participant. As of protocol v9.0, all sites are requested to complete data collection by 31st January 2024. Some participant visits may need to be brought forward.

8.13 COVID-19

Additional site lockdowns

If additional local lockdowns occur during the trial, there are several changes that can be implemented (if required) to try and ensure participant safety and compliance with the trial protocol:

Study visits

It is expected that participant visits will take place as per protocol schedule. However, if a face to face visit is not taking place due to COVID-19 restrictions or lockdowns, the PI^a will contact the patient at the time of the original scheduled visit (3 monthly), and carry out feasible assessments (i.e. SAE check, concomitant medication check, dose evaluation, medication counselling, remote completion of questionnaires and arrange laboratory safety assessments). Follow up calls will take place as per protocol for weeks 1-11.

Participant weight/dose calculation

To ensure participants and families spend the least amount of time in hospital, participants will not be required to have their weight taken at each of the dose titration visits. Participant weight will be mandatory every 6 months and this weight used to calculate the dosage for the next 6 months of study IMP.

Study medication

If required and where possible study medication will be prescribed in 6 month intervals. This will ensure that less time is required for the study visits. It will also be discussed with sites whether the study IMP can be couriered/posted to participants via recorded delivery.

Laboratory Safety Assessments

Participant safety bloods will still be required at the 3 monthly intervals. Sites can discuss whether these safety bloods can be taken by the participant's GP or local paediatrician, but only where these results are readily available to the study team. If sites wish to utilise local GPs/ local paediatricians for safety bloods, they must notify the central team in advance, where possible, so the appropriate set up processes can be completed.

Under extenuating circumstance, If safety bloods cannot be completed, it will be considered if it is appropriate for the participant to be withdrawn from IMP. Each case will be reviewed on an individual basis by the CI, Sponsor and the TMG, and it will be decided whether it would be appropriate to restart the participants IMP, once safety bloods become feasible. The IDMC may also be consulted.

COVID-19 Isolation

It is expected that participant visits will take place as per protocol schedule. However, if a participant or someone they live with has symptoms or has tested positive for COVID-19 and is required to self-isolate, the study visit window can be extended by 2 weeks.

9 TRIAL MEDICATION

9.1 Name and Description of IMP

For the purposes of this trial Tegretol[®] 100mg, 200mg and 400mg Immediate release tablets and Tegretol[®] 100mg/5ml liquid will be classed as IMP.

Tegretol[®] is a brand of carbamazepine licensed for use in the UK and in the countries of all participant sites for this trial. Tegretol[®], rather than generic brands, will be used for consistency across all trial sites during both Stage 1 and Stage 2 of the trial. The use of of generic and controlled release formulations are not permitted for use in this trial. Non-UK sites should source the appropriate strengths available to them to accommodate the prescribed dose.

Tegretol[®] is currently licensed for the treatment of epilepsy, neuropathic pain and prophylaxis of manic-depressive psychosis in patients unresponsive to lithium therapy.

Where possible, sites are to use sugar free formulations of the IMP.

UK Marketing Authorisation Holder for Tegretol[®]: - Novartis Pharmaceuticals UK Limited, Trading as Geigy Pharmaceuticals, [name].

9.1.1 Reference Safety Information

Section 4.8 of the approved SmPCs (PI^b for Australia) for Tegretol[®] 100mg, 200mg and 400mg tablets and Tegretol[®] 100mg/5ml liquid will be used as RSI for this trial. The manufacturer may update the SmPCs (PI^b for Australia) for this IMP. The NCTU/Sponsor/CI will monitor and review changes to the SmPC (PI^b for Australia) to consider the impact on the trial and will revise documentation if required.

Serious Adverse Reactions (SARs) that are thought to have a causal relationship to Tegretol[®] must be assessed for expectedness against the RSI outlined above only.

In the event of a SAR, which is thought to have occurred due to a reaction with the IMP, please also ensure to check section 4.5 'interaction with other medicinal products and other forms of interaction', of the SmPCs (PI^b for Australia) for Tegretol[®] detailed above.

9.2 Drug Storage and Supply

All IMP will be stored as per SmPCs (PI^b for Australia). Once dispensed, participants shall refer to the storage requirements specified on the product label and/or the Patient Information Leaflet provided.

Participating sites will source IMP as per their own local arrangements. Please refer to the current version of the MCDS-Therapy Pharmacy Manual/IMP Guidance document for further details.

9.3 Preparation and Labelling of IMP

Trial IMP will be taken from existing hospital stock and labelled for the trial in accordance with Annex 13 (EU labelling requirements). Participating sites must ensure that the labelling of the IMP is Annex 13 compliant or equivalent depending on country specific regulations. Please consult the MCDS-Therapy Pharmacy Manual/IMP Guidance document for further details.

9.4 Dosage Schedule & Modifications

Tegretol® 100mg, 200mg and 400mg tablets (immediate release) - Tegretol® is to be given orally, with the dose to be used during Stage 2 (treatment) confirmed during Stage 1 (dose titration & tolerability). Anticipated dosage is expected to be between 5-20mg/kg bodyweight daily, to be administered in two divided doses. Tegretol® may be taken during, after or between meals, with a little liquid e.g. a glass of water.

Tegretol® 100mg/5ml liquid (oral suspension) - Tegretol® liquid is to be given orally, with the dose to be used during Stage 2 (treatment) confirmed during Stage 1 (dose titration & tolerability). Anticipated dosage is expected to be between 5-20mg/kg bodyweight daily, to be administered in two divided doses. Tegretol® liquid should be shaken before use and may be taken during, after or between meals.

For stage 1 participants, dosing will be in accordance with the dose titration regimen outlined in section 8.8. CBZ dose to be used in Stage 2 treatment stage will be confirmed during Stage 1 (dose titration & tolerability) see section 8.8.

Participants and their parent(s)/legal guardian(s) will be able to discuss their preference regarding choice of tablet or liquid preparation with their clinician, choice will likely be influenced by participant age. The chosen preparation will be noted on the eCRF trial MACRO database. Stage 2 participants will receive Tegretol[®] for a 12 month period; with the last study visit occurring no later than 31st January 2024. Dosage will be calculated according to the participant's weight. As the trial is recruiting paediatric participants, participants will be weighed every 3 months during Stage 1 and Stage 2 as part of the physical examination and dose adjusted accordingly to ensure the appropriate dose is given to the participants as they grow. For Stage 2 participants CBZ will be titrated as indicated by the outcome of Stage 1.

For advice to be given regarding missed doses please see section 8.8.4.

9.5 Known Drug Reactions and Interactions

All relevant information relating to drug interactions can be found in section 4.5 of the Tegretol[®] SmPC (PI^b for Australia).

Tegretol[®] may lower the plasma level, diminish or even abolish the activity of certain drugs. A list of drugs whose plasma levels may be affected by Tegretol[®] can be found in section 4.5 of the SmPC (Pl^b for Australia) for Tegretol[®]. Of particular note, Tegretol[®] may lower the plasma level, diminish or even abolish the activity of hormonal contraceptives. Therefore, alternative contraceptive methods should be considered.

9.5.1 Special warnings associated with Tegretol[®] use

Special warnings associated with Tegretol[®] use are described in section 4.4 of the Tegretol[®] SmPC (Pl^b for Australia). Participants and their parent(s)/legal guardian(s) will receive the Tegretol[®] Patient Information Leaflet outlining the IMP side effects as part of their medication counselling.

9.6 Concomitant Medications

A complete listing of all concomitant medication received during the trial, from Day 0 baseline observation through to last day IMP taken. will be recorded in the eCRF within the trial MACRO database, the Baseline, Dose Titration or Stable Dose Diary and the participant notes.

9.7 Assessment of Compliance

Participants will be taking trial IMP for up to 24 months (Stage 1: 24 months; Stage 2: 12 months). Eligible Stage 1 participants will also be offered an additional, optional, 12 months of treatment with CBZ after they complete 24 months of treatment. The last patient last visit must take place no later than 31st January 2024. Compliance regarding IMP will be checked weekly via telephone calls during the dose titration period (for up to 12 weeks) and at participant visits held every three months during the dose titration and treatment periods. IMP compliance will be recorded on the eCRF, within the trial MACRO database.

Participants will return all unused IMP and all IMP packaging to their trial team at site at every trial visit. The returned IMP and packaging will be held in the Pharmacy Department at site. Pharmacy will count and record all returns received from each participant on the trial accountability log. An accountability check will also be performed as part of on-site monitoring visits and during dose evaluation calls during the dose titration & tolerability stage.

9.8 Vitamin D

Vitamin D levels will be measured every three months during the dose titration and treatment period as specified in the schedule of events (Tables 6,7 & 9). In the event a participant displays signs of vitamin D insufficiency or deficiency, the participant will be prescribed vitamin D as required. Vitamin D dosing and treatment duration will be appropriate to the need of the patient, follow local guidance for vitamin D insufficiency and deficiency and will be in line with the Fultium SmPC (PI^b for Australia). Only participants identified as having vitamin D deficiency or insufficiency will be prescribed vitamin D. Vitamin D will be sourced from existing hospital stock and stored as per SmPC (PI^b for Australia). Participants and/or their parent(s)/legal guardian(s) will be able to discuss their preference regarding choice of capsules or drops with their clinician, choice will likely be influenced by participant age. The chosen preparation will be noted on the eCRF trial MACRO database.

The preferred brand/formulation for the trial is Fultium D3 800 IU capsules and Fultium D3 drops, However, sites can use suitable alternatives according to local policies and guidelines.

10 PHARMACOVIGILANCE

10.1 Definitions

Term	Definition
Adverse Event (AE)	Any untoward medical occurrence in a participant to whom a medicinal product has been administered, including occurrences which are not necessarily caused by or related to that product.
Adverse Reaction (AR)	An untoward or unintended response in a participant to an investigational medicinal product which is related to any dose administered to that participant.

	The phrase "response to an investigational medicinal product" means that a causal relationship between a trial medication and an AE is at least a reasonable possibility i.e. the relationship cannot be ruled out.
	All cases judged by either the reporting medically qualified professional or the Sponsor as having a reasonable suspected causal relationship to the trial medication qualify as adverse reactions
Reference Safety	The RSI is a list of medical terms detailing the ARs that are expected for an
Information (RSI)	IMP and must be referred to when assessing a SAR for expectedness.
Serious Adverse Event (SAE)	 A serious adverse event is any untoward medical occurrence that: Results in death Is life-threatening* Requires inpatient hospitalisation or prolongation of existing hospitalisation Results in persistent or significant disability/incapacity Consists of a congenital anomaly or birth defect Other important medical events that jeopardise the participant or require intervention to prevent one of the above consequences * - life-threatening refers to an event in which the participant was at immediate risk of death at the time of the event; it does not refer to an event which hypothetically might have caused death if it were more severe.
Serious Adverse Reaction (SAR)	An adverse event that is both serious and, in the opinion of the reporting investigator, believed with reasonable probability to be due to one of the trial treatments, based upon the information provided.
Suspected Unexpected Serious Adverse Reaction (SUSAR)	A serious adverse reaction, the nature and severity of which is not consistent with the approved Reference Safety Information.

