4.4.3 Additional secondary analyses

Use of surgical interventions to manage the condition will be captured on the eCRF over the whole follow up period. These will be reported descriptively as the type and proportion of participants experiencing an event per three month period from baseline until the end of trial follow up.

5 Safety

Laboratory safety assessments outside the appropriate local normal reference range will be reported at a participant level. Abnormal physical examinations will be reported at a participant level together with any further details provided.

All AEs occurring from the point of consent to the end of trial participation are recorded in the trial MACRO database eCRF. AEs are assessed for their relationship to treatment and coded as: Unrelated, Unlikely, Possible, Probable, Definitely, or Not assessable. Severity is graded according to the Common Terminology Criteria for Adverse Events (CTCAE), Version 5.0, Published: November 27, 2017.

Grading is based on the following general guideline:

- **Grade 1 Mild**; asymptomatic or mild symptoms; clinical or diagnostic observations only; intervention not indicated.
- **Grade 2 Moderate**; minimal, local, or non-invasive intervention indicated; limiting age-appropriate instrumental Activities of Daily Living (ADL).
- **Grade 3 Severe** or medically significant but not immediately life-threatening; hospitalization or prolongation of hospitalization indicated; disabling; limiting self-care ADL.
- Grade 4 Life-threatening consequences; urgent intervention indicated.
- Grade 5 Death related to AE.

AEs are coded using the Medical Dictionary for Regulatory Activities (MedDRA) version 22.0. The Clinical Data Management System (CDMS) auto-codes the majority of AEs to the latest version of the MedDRA dictionary. If this is not possible, AEs are coded from the MedDRA dictionary by the Cl.

SARs occurring from the first participant's dose of IMP to the last participant's end of follow-up are recorded on the trial MACRO database eCRF. Following this defined active monitoring period for SARs, investigators are still required to report any SARs or SUSARs which are brought to their attention.

For each SAE the following information is collected:

- 1. Full details in medical terms and case description
- 2. Event duration (start and end dates, if applicable)
- 3. Action taken
- 4. Outcome
- 5. Seriousness criteria
- 6. Causality in the opinion of the investigator

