5.1.1 Adverse events

The number of adverse events and adverse reactions (those possibly, probably or definitely related to treatment) and the worst grade AE and AR per participant will be summarised descriptively.

Example table: Number of events per participant

	Mean (SD)	Median (Q1, Q3)	Min, Max
All adverse events			
Adverse reactions (possibly, probably, definitely)			

Example table: Worst grade reported per participant (number, %)

	None	Mild	Moderate	Severe
All adverse events				
Adverse reactions (possibly, probably, definitely)				

The number of participants reporting each type of adverse event (by MedDRA System Organ Class) will be tabulated.

Example table: Number and percentage of participants affected by each adverse event, reported by System Organ Class

Event term		Total		Mild		Moderate		Severe	
	Ν	%	Ν	%	Ν	%	Ν	%	
Blood and lymphatic system disorders									
Cardiac disorders									
Endocrine disorders									
Eye disorders									
Gastrointestinal disorders									
General disorders and administration site conditions									
Immune system disorders									
Infections and infestations									
Injury, poisoning and procedural complications									
Investigations									
Metabolism and nutrition disorders									

The number and percentage of patients experiencing at least one high grade event (grade 3/4/5).

A line listing of all AEs will be reported, by participant, including severity, seriousness and relationship to study treatment.

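### Protocol 10.1 sets a stricter causality test for serious adverse reactions than for adverse reactions, so a serious event rated possible, or suspected only by the Sponsor, can fall outside SAR and SUSAR classification

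*Protocol*

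**What the plan says.** Protocol 10.1 defines the safety terms in one table.

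- **Adverse reaction.** The test is that "a causal relationship between a trial medication and an AE is at least a reasonable possibility i.e. the relationship cannot be ruled out". Two parties can make that judgement: "All cases judged by either the reporting medically qualified professional or the Sponsor as having a reasonable suspected causal relationship" qualify.
- **Serious adverse reaction.** "An adverse event that is both serious and, in the opinion of the reporting investigator", is "believed with reasonable probability to be due to one of the trial treatments, based upon the information provided". The row does not refer back to the AR definition and does not mention the Sponsor.
- **SUSAR.** "A serious adverse reaction, the nature and severity of which is not consistent with the approved Reference Safety Information".

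SAP section 5 records the relationship to treatment on a six-point scale, "coded as: Unrelated, Unlikely, Possible, Probable, Definitely, or Not assessable". SAP 5.1.1 then counts "adverse reactions (those possibly, probably or definitely related to treatment".

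**The concern.** A serious adverse reaction would normally be an adverse reaction that is also serious. Here the serious version has its own causality test, which asks for probability instead of possibility and names only one judge instead of two. The stricter test therefore applies to the more important events.

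The SAR label controls later steps. Expectedness is assessed against the Reference Safety Information for SARs (protocol 9.1.1, 10.1 and 10.4.2). Sites escalate when they think a SAR may be a SUSAR, and SUSAR status starts the 7-day and 15-day regulatory clocks and the notice to all principal investigators (10.3). If a serious event stops short of the SAR definition, nothing in the definitions carries it into that chain. The drug is being given to children in an indication where it has not been studied before.

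**Working it through.** No arithmetic applies. The check is to run three kinds of serious, unexpected event through the definitions as worded.

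| Serious, unexpected event | AR under 10.1? | SAR under 10.1, read literally? | SUSAR? |
|---|---|---|---|
| Investigator codes Probable or Definitely | Yes | Yes | Yes |
| Investigator codes Possible | Yes; SAP 5.1.1 agrees | No: possible is less than reasonably probable | No, because a SUSAR must first be a SAR |
| Only the Sponsor suspects the drug | Yes, by the Sponsor route | No: the row rests on the reporting investigator's opinion | No, for the same reason |

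The second row assumes that Possible lies below reasonable probability. No text maps the six codes to the SAR definition, but the scale has a separate Probable category, so this is the natural reading. On it, one of the three codes that the SAP treats as related falls between the two definitions.

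**Does another role close the gap?** Protocol 10.4.1 gives causality to the site principal investigator. Section 10.4.2 gives it to the Chief Investigator only where a local assessment could not be obtained. Section 10.4.3 lists an expectedness assessment for the UK Sponsor, but no causality assessment. None of these restores the Sponsor route for SARs.

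**Do the reporting rules close the gap?** Protocol 10.2 has to be read by period.

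1. From consent until the child's participation ends, every UK SAE goes to the trials unit within 24 hours, whatever its causality. The SAE form asks about expectedness when a causal link is suspected. That is the lower test, so an event coded Possible could be picked up here.
2. After that child's participation ends, the SAE duty stops. The SAR duty runs on until the last participant finishes follow-up.
3. After that, investigators must still report SARs and SUSARs that come to their notice, but not SAEs in general.

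In periods 2 and 3 the SAE route has gone, and the wording of the SAR row alone decides whether a serious event must be reported.

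**Do the planned outputs lose anything?** SAP 5.1.1 lists every adverse event with severity, seriousness and relationship. SAP 5.1.2 counts SAEs and lists them with relationship to treatment. A serious event coded Possible appears in the adverse event listing, the AR count and the SAE listing. A recorded event that only the Sponsor suspects appears at least in the adverse event and SAE listings. None of these outputs uses the SAR definition.

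**The case against.** The strongest reply is that the protocol runs on suspicion in practice. The expectedness item on the SAE form is triggered by a suspected link, 9.1.1 describes SARs in terms of a thought-to-be-causal relationship, and the S in SUSAR stands for suspected. The AR row also covers all cases judged by reporter or Sponsor, with no exception for serious ones. This shows that the lower test was probably intended, and careful staff may well apply it. It does not cure the definition. It adds a further formulation that disagrees with the SAR row, and it does not help once the SAE duty has ended.

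A second reply is that the Appendix 1 safety reporting diagram may state a working causality rule. It was not available for this review, so that remains open. For non-UK sites, SUSAR reporting follows local requirements (10.3), so the effect there cannot be judged from these documents.

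A reader might infer three stronger things that the documents do not support.

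- **That serious events would disappear from the safety data.** They would not: UK SAEs are reported during participation whatever their causality, and the interim safety data for the IDMC include all adverse events (protocol 11.2.3).
- **That the SAP would under-count SARs.** The SAP plans no SAR count.
- **That an event coded Possible could never become a SUSAR.** The expectedness question on the SAE form leaves a route, so such an event can be missed but need not be.

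**Conclusion.** The point holds: the SAR definition is wrong as written, and the defect is minor. Protocol 10.1 contradicts itself on the degree of causality required and on who may judge it, and the SUSAR definition inherits the stricter version. What is exposed is SAR and SUSAR classification, the expedited reporting that follows from it and, after a child's participation ends, the duty to report at all. Event capture during participation and the SAP's safety outputs are not affected.

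The size cannot be put as a number of events, because the documents give no rates of serious events and no split by causality code. The conclusion rests on reading the SAR row literally, on placing Possible below reasonable probability, and on Appendix 1 not stating a different rule.

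**What to change.** In protocol 10.1, define a SAR as an adverse reaction, under the protocol's own AR definition and as judged by the reporting medically qualified professional or the Sponsor, that also meets a seriousness criterion. The SUSAR definition then inherits the lower test without further change. Add one sentence stating that Possible, Probable and Definitely count as related, as SAP 5.1.1 already does. Check that Appendix 1 says the same. SAP 5.1.2 needs no new SAR count.

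The SAP is dated 8 February 2024, after the last-visit limit of 31 January 2024. It would therefore be sensible also to check whether any SAE coded Possible, or suspected only by the Sponsor, went without SAR classification and an expectedness assessment. With 40 planned participants that is a short check.

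The cost is one definition line and one sentence. The downside is that a few more serious events may need an expectedness assessment.
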